### **10.6 Response Review**

All responses will be reviewed by an expert(s) independent of the study at the study's completion. Simultaneous review of the patients' files and radiological images is the best approach.

## **11. STATISTICAL CONSIDERATIONS**

### **11.1 Study Design/Sample Size Justification**

This two-arm, phase II study will enroll patients with melanoma or NSCLC who have untreated brain metastases. Subjects with melanoma must have at least 1 brain lesion that requires immediate local therapy that is amenable to surgical resection or LITT, and at least 1 brain lesion that does not require immediate local therapy and can be assessed for response. In certain situations, one lesion can be biopsied and then assessed for response. Subjects with NSCLC are only required to have at least 1 brain lesion that does not require immediate local therapy and can be assessed for response. Subjects will undergo local therapy to 1 or more brain metastases (required for subjects with melanoma, optional for those with NSCLC), followed by treatment with MK-3475.

The primary goal of this study is to determine the efficacy of MK-3475 in patients with untreated brain metastases from melanoma or NSCLC. The primary endpoint is the brain metastasis response rate (BMRR). A drug with minimal activity would be expected to have a BMRR of 10%. Alternatively, MK-3475 will be considered worthy of further study in patients with untreated brain metastases if its true BMRR is similar to the systemic response rate with MK-3475 which is 38% for melanoma and 25% for NSCLC.  and internal data.

### **Power and Sample Size**

**Melanoma Arm**

The melanoma arm will enroll a minimum of 8 subjects. If at least one of the first 8 has a brain metastasis response, a sequential monitoring procedure will be used to evaluate efficacy and futility simultaneously, based on the number of subjects with a confirmed or unconfirmed response according to the rules outlined in Figure 1, Table 8 and Table 9. Only patients who remain on treatment for at least 12 weeks will be considered evaluable for the futility analysis. Accrual will not be suspended during the interim evaluation. Subsequent decisions for pursuing future interim evaluations will be based on the boundaries identified by the sequential monitoring procedure. We will enroll an approximate maximum of 20 subjects in this arm.

[figure not shown]
With an approximate maximum of 20 subjects enrolled, we will have 86% power to demonstrate that the best brain metastasis response rate exceeds 10% at an overall one-sided 10% alpha-level, if the true best brain metastasis response rate is 38%. The calculation is based on the binomialSPRT function in the gsDesign package.

For the final analysis, the response assessment will be based on confirmed best brain metastasis response rate. The adjusted p-value and repeated confidence interval will be computed using sequential methods outlined by Jennison and Turnbull (2000). The minimum criterion for success is that the lower bound of the repeated CI > 10%. Given the null hypothesis underlying the true rate, this may occur when at least 6/20 subjects develop a confirmed brain metastasis response.

If the efficacy boundary is crossed at any time during the trial, enrollment may still continue to 20 subjects and subsequent trial planning may be initiated.

Operating characteristics are shown in Table 10.

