**Table 10. Operating Characteristics of Sequential Monitoring Approach for Melanoma Arm**

True RR	Probability of Declaring Futility	Probability of Go at end of Study	Average Sample Size
10%	0.93	0.05	10.3
15%	0.79	0.16	12.3
20%	0.61	0.32	14.3
25%	0.43	0.50	16.1
30%	0.27	0.66	17.4
35%	0.16	0.80	18.4
40%	0.09	0.89	19.1
45%	0.05	0.94	19.5
50%	0.02	0.97	19.7

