**Non-Small Cell Lung Cancer Arm****Cohort 1:**

The non-small cell lung cancer arm will enroll a minimum of 18 patients into Cohort 1. Following the time that the first 18 subjects have had at least 2 brain metastasis responders, a sequential monitoring procedure will be used to evaluate for efficacy and futility simultaneously, based on the number of subjects with a confirmed or unconfirmed brain metastasis response according to the rules outlined in Figure 2, Table 10, and Table 11. Only patients who remain on treatment for at least 12 weeks will be considered evaluable for the futility analysis. Accrual will not be suspended during the interim evaluation. Subsequent decisions for pausing enrollment and pursuing future evaluations will be based on the boundaries identified by the sequential monitoring procedure. A maximum of 44 subjects will be enrolled in this arm.

With a maximum of 44 patients enrolled in Cohort 1, we will have approximately 80% power to demonstrate that the best brain metastasis response rate exceeds 10% at an overall one-sided 10% alpha-level, if the true best brain metastasis response rate is 25%. The calculation is based on the binomialSPRT function in the gsDesign package.

For the final analysis, the response assessment will be based on confirmed best brain metastasis response rate. The adjusted p-value and repeated confidence interval will be computed using sequential methods outlined by Jennison and Turnbull (2000). The minimum criterion for success is that the lower bound of the repeated CI > 10%. Given the null hypothesis underlying the true rate, this may occur when at least 10/44 subjects develop a confirmed response.

[figure not shown]
If the efficacy boundary is crossed at any time during the trial, enrollment may still continue to 44 subjects and subsequent trial planning may be initiated.

Operating characteristics are shown in Table 13.

Cohort 2:

A maximum of 10 patients with NSCLC will be enrolled in Cohort 2. These patients will meet the same eligibility requirements as other NSCLC patients, except for the following: they will be required to have had at least 1 prior platinum-based systemic therapy, and they must either be negative or unevaluable for PD-L1 expression. The response rate with MK-3475 in PD-L1 negative patients in a previous trial is 9%, however the efficacy in brain metastases is unknown. Therefore this cohort will be exploratory in nature.

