**Table 13. Operating Characteristics of Sequential Monitoring Approach for NSCLC Arm**

True RR	Probability of Declaring Futility	Probability of Go at end of Study	Average Sample Size
10%	0.87	0.05	24.9
15%	0.58	0.25	32.2
20%	0.29	0.55	38.1
25%	0.12	0.80	41.5
30%	0.04	0.93	43.1
35%	0.01	0.98	43.7

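### The futility count drops patients who leave treatment before 12 weeks, but the operating characteristics in Tables 10 and 13 make no allowance for that exclusion

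*Combined protocol and SAP*

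**What the plan says.** Section 11.1 sets a sequential rule for each arm, with efficacy and futility judged together on confirmed or unconfirmed brain metastasis responses. Under both Melanoma Arm and Non-Small Cell Lung Cancer Arm, Cohort 1, it adds: "Only patients who remain on treatment for at least 12 weeks will be considered evaluable for the futility analysis". No such restriction is stated for efficacy.

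The maxima are given as enrolled patients: "We will enroll an approximate maximum of 20 subjects in this arm" and "A maximum of 44 subjects will be enrolled in this arm". The power statements (86% and about 80%) also refer to patients enrolled.

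The bounds in Tables 8, 9, 11 and 12 are indexed by number of subjects. Table 10 ("Operating Characteristics of Sequential Monitoring Approach for Melanoma Arm") and Table 13 ("Operating Characteristics of Sequential Monitoring Approach for NSCLC Arm") have columns for true response rate, futility probability, Go probability and average sample size. Neither set of tables says whether subjects are enrolled or 12-week patients. The plan gives no expected share leaving before 12 weeks and no replacement rule. It does not say whether 12-week evaluability applies to the first 8 or 18.

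Section 11.4.2 puts all eligible patients in the main response analysis and treats progression, early death and unknown status as treatment failures.

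**The concern.** Sections 4.1 and 4.7 let patients leave treatment early for progressing or threatening brain lesions, and death also ends treatment. Patients who leave before 12 weeks for these reasons are mostly non-responders. Taking them out of the futility count raises the apparent response rate in the set meant to detect inactivity. The same patients count as failures in the final analysis.

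If the printed tables ignore this, their readers are told that an inactive drug will be stopped more often, and after fewer patients, than the written rule delivers. That matters in a population with untreated brain metastases, because futility is the only boundary whose crossing ends accrual. Crossing the efficacy boundary lets enrolment continue.

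**Working it through.** **Inputs from section 11.1.** The inactive rate is 10%; the target rates are 38% (melanoma) and 25% (NSCLC). First looks are at 8 and 18, and maxima are 20 and 44.
- Futility if responders are at or below, melanoma (Table 9): 0 at 8; 1 at 9-13; 2 at 14-17; 3 at 18-20.
- NSCLC (Table 12), from the first look: 1 at 18-20; 2 at 21-26; 3 at 27-32; 4 at 33-38; 5 at 39-44.
- Efficacy bounds are as in Tables 8 and 11.

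**Step 1: reproduce the printed tables.** I used an exact binomial recursion with a look after each counted patient and nobody excluded. Futility stops the arm; an efficacy crossing does not. Go means crossing the efficacy bound before any futility stop.

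| Row | Computed futility / Go / mean N | Printed |
|---|---|---|
| Melanoma 10% | 0.931 / 0.053 / 10.33 | 0.93 / 0.05 / 10.3 |
| Melanoma 40% | 0.091 / 0.887 / 19.12 | 0.09 / 0.89 / 19.1 |
| NSCLC 10% | 0.866 / 0.054 / 24.89 | 0.87 / 0.05 / 24.9 |
| NSCLC 25% | 0.121 / 0.797 / 41.52 | 0.12 / 0.80 / 41.5 |

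The other rows of both tables agree as well. The tables therefore describe one sequence of counted patients up to 20 or 44, with no allowance for exclusions.

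**Step 2: see the direction by hand.** Let p be the all-patient response rate and d the share leaving before 12 weeks. If leavers never respond, the rate among counted patients is p/(1 - d) = 0.10/0.80 = 0.125 at d = 20%.
- Melanoma, chance of 0 responders in 8 counted: 0.9^8 = 0.430 becomes 0.875^8 = 0.344.
- NSCLC, chance of at most 1 in 18 counted: 0.9^18 + 18 × 0.1 × 0.9^17 = 0.450 becomes 0.875^18 + 18 × 0.125 × 0.875^17 = 0.323.

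**Step 3: apply the written rule in full.** Futility is counted on 12-week patients, efficacy on all enrolled, and enrolment is capped at 20 and 44. The value of d is an assumption. Model A: leavers never respond (the extreme case). Model B: leaving is independent of response.

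Futility probability at a true rate of 10%:

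| d | Melanoma A | Melanoma B | NSCLC A | NSCLC B |
|---|---|---|---|---|
| 0 (printed) | 0.93 | 0.93 | 0.87 | 0.87 |
| 5% | 0.92 | 0.93 | 0.84 | 0.87 |
| 10% | 0.89 | 0.91 | 0.80 | 0.85 |
| 20% | 0.81 | 0.88 | 0.68 | 0.82 |

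Mean enrolled at the decision with d = 20%, when the first look waits for 8 or 18 evaluable patients, is 12.4 (B) to 13.2 (A) in melanoma and 29.4 (B) to 32.4 (A) in NSCLC. If the first gate counts the first 8 or 18 enrolled, the Model A figures fall to 12.1 and 29.0.

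**Step 4: effects in the other direction, d = 20%.** Wrongful stopping of an active drug falls. In melanoma at 38% it goes from 0.116 to 0.031 (A) or 0.106 (B). In NSCLC at 25% it goes from 0.121 to 0.030 (A) or 0.111 (B). The Go probability at 10% barely moves: 0.053 to at most 0.055, and 0.054 to at most 0.056.

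**Step 5: the alternative reading.** Suppose subjects means 12-week patients, the true rate is the rate among them, and leavers are replaced. The printed stopping probabilities then hold exactly. Reaching 20 or 44 such patients at d = 20% takes 20/0.80 = 25 and 44/0.80 = 55 enrolled. The mean enrolled at 10% is 10.33/0.80 = 12.9 and 24.89/0.80 = 31.1.

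**The case against.** **A reader might infer that the tables can be reproduced only by counting every enrolled patient.** They cannot be read that strictly. The arithmetic fits 12-week patients with replacement equally well (step 5). What argues against that reading is the text: both maxima and both power statements are in enrolled patients, and replacement would exceed 44. The melanoma maximum is only approximate. Figures 1 and 2 are missing from the text available here, so nothing can be drawn from their labels.

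**The effect could be small.** This stands in part. Entry requires a life expectancy of at least 3 months and ECOG below 2, and excludes symptomatic brain metastases and leptomeningeal disease (sections 3.1 and 3.2). Sections 4.8 and 5.2 allow treatment to continue while progression is being confirmed or after local therapy. Response is first assessed at 8 weeks and unconfirmed responses count, so a responder who stops between weeks 8 and 12 is also dropped. The truth therefore probably lies between Models A and B. At 5% loss, Model B shows no change at two decimals.

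**A weaker futility rule may be a deliberate protection of an active drug.** That is a defensible choice, and step 4 shows the gain. It does not explain why the printed figures omit the cost.

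**A reader might also infer a higher false-positive risk.** The plan does not support this. The restriction is stated for futility only, and the final criteria of 6/20 and 10/44 are unchanged.

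**Conclusion.** The concern holds as a mismatch between a stated rule and its stated performance. With the enrolment maxima as written, the 12-week condition makes a futility stop for an inactive drug less likely than Tables 10 and 13 say, and raises the average number enrolled. If the tables refer instead to 12-week patients with replacement, the stopping probabilities are right, but the average sample sizes and maxima are not numbers enrolled.

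Under the enrolment maxima, the direction is the same in both loss models. The size is conditional, because the documents give no early-loss rate. It is slight at 5% loss. At 20% loss it is a drop of about 0.05 to 0.13 in melanoma and 0.05 to 0.19 in NSCLC, where the larger figure is the extreme in which no early leaver responds. The harm is limited: enrolment is capped, the false-positive risk is essentially unchanged, and wrongful stopping of an active drug falls. This should be fixed, but it does not undermine the final analysis.

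**What to change.** In both arms, replace the sentence with wording such as: all treated patients with at least 12 weeks of potential follow-up since first dose are evaluable for futility; those who die, progress or stop treatment earlier without a brain metastasis response count as non-responders, as in section 11.4.2. Use the same denominator for the efficacy boundary, since crossing it means that "subsequent trial planning may be initiated". The stopping probabilities in Tables 10 and 13 then describe the rule.

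If the 12-week condition is to stay, say that the bounds, the first gate and the tables refer to 12-week evaluable patients. Then recompute Tables 10 and 13 and the enrolment maxima under a stated early-loss range.

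The first option costs one sentence per arm, needs no new data and keeps the 12-week window. It has two downsides. Early stops unrelated to the drug count against it, as they already do in the main analysis. The chance of wrongly stopping an active drug also returns to the level implied by the tables, about 0.12 in each arm at its target rate.

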**Figure 1. Sequential Monitoring Rules for Efficacy and Futility in Melanoma Arm**

**Table 8. Decision Rules based on Efficacy Bounds for Melanoma Arm**

Monitoring Point (# subjects)	Minimum # Responders to Determine Efficacy
8	3
9-12	4
13-17	5
18-20	6

**Table 9. Decision Rules based on Futility Bounds for Melanoma Arm**

Monitoring Point (# subjects)	Maximum # subjects w/ response to declare Futility
8	0
9-13	1
14-17	2
18-20	3

**Table 10. Operating Characteristics of Sequential Monitoring Approach for Melanoma Arm**

True RR	Probability of Declaring Futility	Probability of Go at end of Study	Average Sample Size
10%	0.93	0.05	10.3
15%	0.79	0.16	12.3
20%	0.61	0.32	14.3
25%	0.43	0.50	16.1
30%	0.27	0.66	17.4
35%	0.16	0.80	18.4
40%	0.09	0.89	19.1
45%	0.05	0.94	19.5
50%	0.02	0.97	19.7

**Non-Small Cell Lung Cancer Arm****Cohort 1:**

The non-small cell lung cancer arm will enroll a minimum of 18 patients into Cohort 1. Following the time that the first 18 subjects have had at least 2 brain metastasis responders, a sequential monitoring procedure will be used to evaluate for efficacy and futility simultaneously, based on the number of subjects with a confirmed or unconfirmed brain metastasis response according to the rules outlined in Figure 2, Table 10, and Table 11. Only patients who remain on treatment for at least 12 weeks will be considered evaluable for the futility analysis. Accrual will not be suspended during the interim evaluation. Subsequent decisions for pausing enrollment and pursuing future evaluations will be based on the boundaries identified by the sequential monitoring procedure. A maximum of 44 subjects will be enrolled in this arm.

With a maximum of 44 patients enrolled in Cohort 1, we will have approximately 80% power to demonstrate that the best brain metastasis response rate exceeds 10% at an overall one-sided 10% alpha-level, if the true best brain metastasis response rate is 25%. The calculation is based on the binomialSPRT function in the gsDesign package.

For the final analysis, the response assessment will be based on confirmed best brain metastasis response rate. The adjusted p-value and repeated confidence interval will be computed using sequential methods outlined by Jennison and Turnbull (2000). The minimum criterion for success is that the lower bound of the repeated CI > 10%. Given the null hypothesis underlying the true rate, this may occur when at least 10/44 subjects develop a confirmed response.

[figure not shown]
If the efficacy boundary is crossed at any time during the trial, enrollment may still continue to 44 subjects and subsequent trial planning may be initiated.

Operating characteristics are shown in Table 13.

Cohort 2:

A maximum of 10 patients with NSCLC will be enrolled in Cohort 2. These patients will meet the same eligibility requirements as other NSCLC patients, except for the following: they will be required to have had at least 1 prior platinum-based systemic therapy, and they must either be negative or unevaluable for PD-L1 expression. The response rate with MK-3475 in PD-L1 negative patients in a previous trial is 9%, however the efficacy in brain metastases is unknown. Therefore this cohort will be exploratory in nature.

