**Figure 2. Sequential Monitoring Rules for Efficacy and Futility in NSCLC Arm**

**Table 11. Decision Rules based on Efficacy Bounds for NSCLC Arm**

Monitoring Point (# subjects)	Minimum # Responders to Determine Efficacy
10-12	4
13-18	5
19-24	6
25-30	7
31-36	8
37-42	9
43-44	10

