**Table 12. Decision Rules based on Futility Bounds for NSCLC Arm**

Monitoring Point (# subjects)	Maximum # subjects w/ response to declare Futility
10-14	0
15-20	1
21-26	2
27-32	3
33-38	4
39-44	5

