## 11.5 Accrual Rate and Study Duration

The plan is to enroll 74 patients total: 20 with melanoma, 44 with NSCLC in Cohort 1, and 10 with NSCLC in Cohort 2. The first interim analysis will be after 8 patients on the melanoma arm, 18 with NSCLC on the NSCLC arm. Our estimated rate of accrual based on current volume and

referral patterns is approximately 4 melanoma patients, 8 NSCLC patients with brain metastases at our institution monthly. Assuming a conservative 50% eligibility rate (based on the relatively high likelihood of screen failures) for the melanoma arm, the overall anticipated time of accrual is approximately 18 months. The eligibility rate for the NSCLC arm will be approximately 20%; accrual will take approximately 36 months.

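### The NSCLC decision tables (Tables 11 and 12) open at 10 patients, but the text puts the first look at 18 and Table 13 as a whole reproduces only from 18

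*Combined protocol and SAP*

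**What the plan says.** Section 11.1, NSCLC arm, Cohort 1: "The non-small cell lung cancer arm will enroll a minimum of 18 patients into Cohort 1". Monitoring is then conditional: "Following the time that the first 18 subjects have had at least 2 brain metastasis responders, a sequential monitoring procedure will be used". The ceiling is 44. Section 11.5 gives the same starting point, "The first interim analysis will be after 8 patients on the melanoma arm, 18 with NSCLC on the NSCLC arm", and Section 4.1 repeats it.

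The decision tables do not follow this:

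- "Table 11. Decision Rules based on Efficacy Bounds for NSCLC Arm" opens with 4 responders at 10-12 patients, then 5 at 13-18.
- "Table 12. Decision Rules based on Futility Bounds for NSCLC Arm" opens with 0 responses at 10-14 patients, then 1 at 15-20.

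Nothing in the plan explains the rows below 18. The melanoma tables (8 and 9) open at 8, exactly where the melanoma text starts.

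Two further statements in the Cohort 1 text matter. For futility, only patients on treatment for at least 12 weeks count, and accrual is not paused for the look. The rules are to be applied "according to the rules outlined in Figure 2, Table 10, and Table 11". Table 10 holds the melanoma operating characteristics. Table 12 is not cited in the NSCLC text.

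**The concern.** Table 13 and the power statement describe one monitoring schedule, and the tables that would be used at a look print a longer one. The operating characteristics depend on when looking begins: every additional early look at a low futility bound is another chance to stop a cohort in which the drug works. Someone who works from the tables alone could apply a rule whose error rates are not those stated.

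The count makes this more than cosmetic. With 18 patients enrolled and accrual continuing, the number who have been on treatment for 12 weeks may be below 18. The column headed as a number of subjects does not say which count it means. A person holding, say, 14 evaluable patients finds a row for 14. The wrong table reference adds to the confusion, because it leads to one correct NSCLC table and one melanoma table, and not to the futility bounds.

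**Working it through.** **Inputs.** From Section 11.1: null rate 10%, alternative 25%, one-sided alpha 10%, power about 80% (so beta 0.20), maximum 44, binomial SPRT. Bounds are as printed in Tables 11 and 12. The target is Table 13.

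**Step 1: are the printed bounds one set of lines?** For a binomial SPRT, let k = ln[p1(1-p0)/(p0(1-p1))] = ln[(0.25 x 0.90)/(0.10 x 0.75)] = ln 3 = 1.0986.

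- Slope = ln[(1-p0)/(1-p1)]/k = ln(0.90/0.75)/1.0986 = 0.1660.
- Lower intercept = ln[0.20/0.90]/k = -1.369.
- Upper intercept = ln[0.80/0.10]/k = 1.893.

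The futility bound is the lower line rounded down and the efficacy bound is the upper line rounded up. At n = 10 the lines are 0.29 and 3.55, giving 0 and 4. At n = 18 they are 1.62 and 4.88, giving 1 and 5. All 35 values of n from 10 to 44 agree with both tables. So rows 10-17 are the same lines carried further left.

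**Step 2: reproduce Table 13.** I used an exact recursion. The distribution of responders is updated one patient at a time, x to x+1 with probability p, and checked against the bounds at every n from the first look onward. Three conventions are needed to match the print:

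- Go is the probability that efficacy is crossed before futility.
- Average sample size counts stopping for futility only, because enrolment may continue after an efficacy crossing.
- Futility is counted on that same basis.

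| True rate | Table 13: futility / Go / average n | First look 18 | First look 10 |
|---|---|---|---|
| 10% | 0.87 / 0.05 / 24.9 | 0.866 / 0.054 / 24.9 | 0.879 / 0.061 / 20.4 |
| 15% | 0.58 / 0.25 / 32.2 | 0.577 / 0.252 / 32.2 | 0.612 / 0.254 / 28.6 |
| 20% | 0.29 / 0.55 / 38.1 | 0.295 / 0.549 / 38.1 | 0.339 / 0.536 / 35.5 |
| 25% | 0.12 / 0.80 / 41.5 | 0.121 / 0.797 / 41.5 | 0.160 / 0.774 / 39.8 |
| 30% | 0.04 / 0.93 / 43.1 | 0.042 / 0.930 / 43.1 | 0.068 / 0.909 / 42.1 |
| 35% | 0.01 / 0.98 / 43.7 | 0.013 / 0.981 / 43.7 | 0.027 / 0.967 / 43.2 |

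A start at 18 reproduces every entry to within rounding; the largest gap in average sample size is 0.03. At 17 the largest gap is already 0.69, at 19 it is 0.56, and at 10 it is 4.5.

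**Step 3: where the difference comes from.** At 25%, moving only the futility looks back to 10 gives Go of 0.768. Moving only the efficacy looks back to 10 gives 0.802. The loss therefore comes from the early futility rows. Applied after every patient, rows 10-17 of Table 12 would declare futility in 10.1% of trials at a true 25% rate. In 6.1 of those 10.1 percentage points the first 18 patients would have included at least 2 responders, so the text would have let the cohort continue.

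**The case against.** The strongest reply is that the text governs. Three statements fix the first look at 18, and sequential monitoring begins only once the first 18 include at least 2 responders. The Table 12 rows for 10-17 fire only at 0 responses, or at most 1, so with 2 counted responders they cannot fire. The early efficacy rows in Table 11 do not stop the cohort either, since crossing that bound leaves enrolment free to run to 44. On this reading the early rows are surplus points and the step 3 figures describe a trial that the text rules out.

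Most of that stands, and it limits the point. It does not remove it. The reply assumes that the 18, the responders and the monitoring points are all counted on the same patients. The plan does not say so, and its 12-week condition gives futility a different denominator. A look with 18 enrolled, 10 to 17 evaluable and 0 or 1 counted responses falls on a printed row that declares futility (0 at 10-14, at most 1 at 15-17). The documents do not allow an estimate of how often that would happen.

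A reader might also infer that the printed tables belong to a different and weaker design. They do not: rows 18-44 are the ones that yield Table 13, and rows 10-17 lie on the same lines. Nor does the 80% power alone identify the start. First looks at 12 and at 14 to 22 all give 0.780 to 0.797, which fits a statement of about 80%. It is Table 13 as a whole that singles out 18.

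**Conclusion.** The point holds as an inconsistency between tables and text on the decision thresholds, with a wrong table reference. Rows 18-44 need no change.

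If the printed rows were used after every patient from the 10th, power at 25% would be about 77% against the reproduced 79.7% (printed 0.80), and false futility would rise from 0.12 to 0.16. Go at a true 10% would be 0.061, still below the stated 10% alpha. These figures measure what ignoring the 18-patient start would cost. They are not the expected behaviour of the trial, and a reader should not conclude that the cohort as planned carries a 16% chance of false futility.

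The result assumes a look after every patient, the printed bounds, and the counting conventions set out above. Figure 2, which is also cited for the rules, was not available to check. Whether the 18 are enrolled or evaluable at 12 weeks cannot be settled from the documents; it is for the sponsor to state.

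**What to change.** 1. Start Table 11 at 18 (5 responders) and Table 12 at 18 (1 response), or keep the earlier rows and mark them as not used.
2. State whether the 18 and the monitoring points count enrolled patients or patients evaluable at 12 weeks, and use the same count in Sections 4.1, 11.1 and 11.5.
3. In the Cohort 1 text of Section 11.1, cite Tables 11 and 12 for the rules in place of Tables 10 and 11, and check that Figure 2 starts at the same point.
4. If looks from 10 are in fact intended, change the statements of 18 in Sections 4.1, 11.1 and 11.5 and restate Table 13 and the power (about 77%; at a 25% rate, futility 0.16 and average sample size 39.8).

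Items 1 to 3 are table and wording corrections: no added patients and no new analysis. Item 4 needs Table 13 recomputed, as in the last column above.

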**11.2 Analytic Plan for Primary Objectives:**

We will use mRECIST criteria to determine brain metastasis response rate (BMRR). The proportion of patients with a brain metastasis response in the clinically evaluable lesion(s) will be calculated along with a 95% confidence interval.

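### The stated power (about 80% NSCLC Cohort 1, 86% melanoma) is the chance of ever touching the efficacy bound; the final success rule has about 67–69% and 80–83%

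*Combined protocol and SAP*

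**What the plan says.** Section 11.1 gives each arm a power statement based on a binomial sequential probability ratio test (SPRT), at an overall one-sided 10% alpha:

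- NSCLC Cohort 1, at most 44 patients, true rate 25%: "we will have approximately 80% power to demonstrate that the best brain metastasis response rate exceeds 10"%.
- Melanoma, at most about 20 patients, true rate 38%: "we will have 86% power to demonstrate that the best brain metastasis response rate exceeds 10"%.

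Tables 10 and 13 tabulate operating characteristics under the column heading "Probability of Go at end of Study".

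The same section then defines success at the end. "For the final analysis, the response assessment will be based on confirmed best brain metastasis response rate". The minimum criterion is a repeated confidence interval with its lower bound above 10%. For NSCLC, "this may occur when at least 10/44 subjects develop a confirmed response"; for melanoma, "this may occur when at least 6/20 subjects develop a confirmed brain metastasis response".

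The interim bounds, by contrast, count confirmed or unconfirmed responses. A crossing does not end the arm: "If the efficacy boundary is crossed at any time during the trial, enrollment may still continue to 44 subjects", and planning of later trials may begin. The melanoma text is parallel, with 20 patients.

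**The concern.** Power should be the probability of meeting the criterion by which the trial will be judged. Here the power comes from a sequential procedure that can be met at any look, whereas the stated criterion is a single confirmed count at the end. Because enrolment may run on after a crossing, an arm can touch the efficacy bound early and still finish below 10/44 or 6/20. Such an arm would count towards the printed power and towards the Go column, yet fail the final criterion. A reader of the power sentences would then underestimate the risk of missing an active drug on the primary endpoint, chiefly in the largest cohort.

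**Working it through.** **Inputs, all from Section 11.1.** Null rate 10%. Alternatives 25% (NSCLC) and 38% (melanoma). First looks at 18 and 8 patients, maxima 44 and 20. Efficacy and futility bounds from Tables 11 and 12 (NSCLC) and Tables 8 and 9 (melanoma). Final counts 10/44 and 6/20. All responses are taken as confirmed, which favours the plan.

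**Step 1: the bounds are SPRT bounds.** With k = ln[p1(1−p0)/(p0(1−p1))] and s = ln[(1−p0)/(1−p1)]/k, the efficacy bound is the smallest integer at or above s·n + ln[(1−β)/α]/k. The futility bound is the largest integer at or below s·n + ln[β/(1−α)]/k. Take α = 0.10 and β = 0.20 (β is inferred, not stated). For NSCLC, k = ln 3 = 1.0986 and s = 0.166. At n = 44 the efficacy value is 7.30 + 1.89 = 9.2, giving 10; the futility value is 7.30 − 1.37 = 5.9, giving 5. Both match the tables, and so does every other monitoring point in both arms.

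**Step 2: reproduce the printed figures.** Let P_n(x) be the probability of x responses among n patients with futility not yet declared. Then P_n(x) = p·P_{n−1}(x−1) + (1−p)·P_{n−1}(x). From the first look onward, states at or below the futility bound are removed, states at or above the efficacy bound are flagged as crossed, and enrolment continues. Define Go as ever flagged.

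| Arm, true rate | Go, recomputed | Go, printed | Average N, recomputed | Average N, printed |
|---|---|---|---|---|
| NSCLC 10% | 0.054 | 0.05 | 24.9 | 24.9 |
| NSCLC 20% | 0.549 | 0.55 | 38.1 | 38.1 |
| NSCLC 25% | 0.797 | 0.80 | 41.5 | 41.5 |
| Melanoma 10% | 0.053 | 0.05 | 10.3 | 10.3 |
| Melanoma 40% | 0.887 | 0.89 | 19.1 | 19.1 |

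Every row of Tables 10 and 13 is matched within 0.005 for both probability columns and 0.07 for average N. At 38% the melanoma value is 0.855, the stated 86%. To match the futility column of Table 10, the futility bound must still apply after an efficacy crossing: at 20% this gives 0.609 (printed 0.61), against 0.594 if it does not. Some simulated arms therefore count in both the futility and the Go column.

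If a crossing ended the arm, average N would be 24.1 for NSCLC at 25% (printed 41.5) and 8.6 for melanoma at 50% (printed 19.7). The tables do not describe that design.

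**Step 3: power of the final rule.** Without futility stopping this is the binomial tail P(X ≥ r | N, p). With futility it is the same recursion, summed over final counts of r or more.

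| Final rule | True rate | Futility binding at every patient | Futility at first and last look only | No futility stop | Stated |
|---|---|---|---|---|---|
| ≥10/44 | 25% | 0.674 | 0.685 | 0.691 | about 0.80 |
| ≥10/44 | 10% | 0.010 | 0.010 | 0.010 | 0.05 (Table 13) |
| ≥6/20 | 38% | 0.797 | 0.827 | 0.833 | 0.86 |
| ≥6/20 | 10% | 0.010 | 0.011 | 0.011 | 0.05 (Table 10) |

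**Step 4: where the difference goes.** A final count of 10/44 is itself on the efficacy bound, so every final success has also crossed. The gap is therefore the arms that cross and then finish short: 0.797 − 0.674 ≈ 0.12 for NSCLC at 25%, and 0.855 − 0.797 ≈ 0.06 for melanoma at 38%. The 10/44 rule reaches 80% power only at a true rate of 27.3% (no futility stop) to 27.7% (binding futility).

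**Step 5: sensitivity to confirmation (assumption).** The documents give no confirmation rate. If the planning rate includes unconfirmed responses and 90% are later confirmed, power falls to 0.53–0.54 (NSCLC) and 0.71–0.73 (melanoma). At 100% it is the range in Step 3.

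**The case against.** The strongest reply is that a crossing is meant to be the success, with enrolment simply continuing. Tables 8 and 11 describe their counts as determining efficacy, a crossing allows later trials to be planned, and this reading fits the printed Go and average-N columns. On it, 80% and 86% would stand. The average-N check rules out only the version in which a crossing closes the arm. What defeats the wider reading is the text: crossings accept unconfirmed responses, whereas the minimum criterion for success is set at the final analysis and on confirmed responses. Nothing says that an earlier crossing satisfies it.

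A second reply is that 10/44 and 6/20 are only counts at which success may occur, the formal rule being the repeated interval, which is not computed here. That is fair. But if those counts are the least that could succeed, the wording can only lower power below 0.691 and 0.833. The counts equal the SPRT bounds at the maximum sample sizes. They are also the smallest whose exact two-sided 95% lower limit exceeds 10% (10/44: 11.5%, against 9.8% for 9/44; 6/20: 11.9%, against 8.7% for 5/20), in line with Section 11.2, where the response proportion "will be calculated along with a 95% confidence interval". That agreement is not proof about the repeated interval: a single-look one-sided 10% limit already exceeds 10% at 8/44 (10.9%) and 5/20 (12.7%).

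It also stands that the printed figures are correct for the SPRT, that false positives are not inflated, and that the melanoma gap is modest.

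**Conclusion.** The concern holds. The SPRT figures are computed correctly but attached to the wrong event: they give the probability of ever crossing the efficacy bound, not of meeting the end-of-study criterion. For NSCLC Cohort 1 the shortfall is 11 to 13 percentage points, so the chance of missing a drug with a true 25% rate is 31–33% rather than 20%. For melanoma the shortfall is 3 to 6 points. The final rule's type I error is about 1%, well below the stated 10%, so the cost is undisclosed false negatives.

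These results take 10/44 and 6/20 as the working form of the final criterion, one response probability throughout, and full confirmation. The 12-week evaluability condition for futility and delayed or less frequent looks are not modelled; the no-futility column bounds the effect of any lighter futility stopping. Importance rests mainly on the NSCLC cohort.

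**What to change.** In Section 11.1, state that success is judged on the final confirmed count and that an earlier crossing alone does not meet it. Restate power as about 67–69% (NSCLC, 25%) and about 80–83% (melanoma, 38%), name the futility assumption used, and give the actual type I error of about 1%.

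Then either relabel the Go columns of Tables 10 and 13 as the probability of ever crossing the efficacy bound, or replace them with values for the final rule (range from binding futility at every look to none):

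| True rate | Table 10 (≥6/20) | Table 13 (≥10/44) |
|---|---|---|
| 10% | 0.01 | 0.01 |
| 15% | 0.06–0.07 | 0.11 |
| 20% | 0.18–0.20 | 0.37–0.38 |
| 25% | 0.35–0.38 | 0.67–0.69 |
| 30% | 0.54–0.58 | 0.88–0.89 |
| 35% | 0.72–0.75 | 0.97 |
| 40% | 0.84–0.87 | – |
| 45% | 0.92–0.94 | – |
| 50% | 0.96–0.98 | – |

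Keep the 6/20 and 10/44 thresholds. If the sponsor does intend an earlier crossing to count as success, the plan must say so and reconcile it with the confirmed-response criterion.

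The cost is the success and power wording for each arm and two table columns. Boundaries, thresholds, sample size and patient procedures are unchanged; the stated power, mainly for NSCLC, becomes less favourable.
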